APPENDIX B. King's Health Questionnaire

Site No.	Subject No.	Subject Initials	Date _____

1 - How would you describe your health at present?
 
 Very good (1)
 
 Good (2)
 
 Fair (3)
 
 Poor (4)
 
 Very poor (5)
			

2- How much do you think your bladder problem affects your life?
 
 Not at all (1)
 
 A little (2)
 
 Moderately (3)
 
 A lot (4)
			

3a- To what extent does your bladder problem affect your household tasks (e.g. cleaning, shopping, etc.)?
 
 Not at all (1)
 
 A little (2)
 
 Moderately (3)
 
 A lot (4)
			

3b- Does your bladder problem affect your job, or your normal daily activities outside the home?
 
 Not at all (1)
 
 A little (2)
 
 Moderately (3)
 
 A lot (4)
			

4a- Does your bladder problem affect your physical activities (e.g. going for a walk, run, sport, gym, etc.)?
 
 Not at all (1)
 
 A little (2)
 
 Moderately (3)
 
 A lot (4)
			

4b- Does your bladder problem affect your ability to travel?
 
 Not at all (1)
 
 A little (2)
 
 Moderately (3)
 
 A lot (4)
			

4c- Does your bladder problem limit your social life?
 
  Not at all (1)  A little (2)  Moderately (3)  A lot (4)

4d - Does your bladder problem limit your ability to see/visit friends?
 
  Not at all (1)  A little (2)  Moderately (3)  A lot (4)

5a- Does your bladder problem affect your relationship with your partner?
 
  Not applicable (0)  Not at all (1)  Slightly (2)  Moderately (3)  A lot (4)

5b- Does your bladder problem affect your sex life?
 
  Not applicable (0)  Not at all (1)  Slightly (2)  Moderately (3)  A lot (4)

5c- Does your bladder problem affect your family life?
 
  Not applicable (0)  Not at all (1)  Slightly (2)  Moderately (3)  A lot (4)

6a- Does your bladder problem make you feel depressed?
 
  Not at all (1)  Slightly (2)  Moderately (3)  Very much (4)

6b- Does your bladder problem make you feel anxious or nervous?
 
  Not at all (1)  Slightly (2)  Moderately (3)  Very much (4)

6c- Does your bladder problem make you feel bad about yourself?
 
 Not at all (1)
 
 Slightly (2)
 
 Moderately (3)
 
 Very much (4)
	

7a- Does your bladder problem affect your sleep?
 
 Never (1)
 
 Sometimes (2)
 
 Often (3)
 
 All the time (4)
	

7b- Do you feel worn out/tired?
 
 Never (1)
 
 Sometimes (2)
 
 Often (3)
 
 All the time (4)
	

8a - Wear pads to keep dry?
 
 Never (1)
 
 Sometimes (2)
 
 Often (3)
 
 All the time (4)
	

8b- Be careful how much fluid you drink?
 
 Never (1)
 
 Sometimes (2)
 
 Often (3)
 
 All the time (4)
	

8c- Change your underclothes when they get wet?
 
 Never (1)
 
 Sometimes (2)
 
 Often (3)
 
 All the time (4)
	

8d- Worry in case you smell?
 
 Never (1)
 
 Sometimes (2)
 
 Often (3)
 
 All the time (4)
	

8e- Get embarrassed because of your bladder problem?
 
 Never (1)
 
 Sometimes (2)
 
 Often (3)
 
 All the time (4)
	

Sign with Participant Initials
	
Date Form Completed :

Calculation of KHQ–QoL domain scores

KHQ–QoL domain scores were calculated using the following formulae.

1. General health perceptions:

$$\text{Score} = ((\text{score to Q1} - 1)/4) \times 100$$

2. Impact on life:

$$\text{Score} = ((\text{score to Q2} - 1)/3) \times 100$$

3. Role limitations:

$$\text{Score} = (((\text{score to Q3a} + \text{Q3b}) - 2)/6) \times 100$$

4. Physical limitations:

$$\text{Score} = (((\text{score to Q4a} + \text{Q4b}) - 2)/6) \times 100$$

5. Social limitations:

if score Q5c ≥ 1 ,

$$\text{Score} = (((\text{score to Q4c} + \text{Q4d} + \text{Q5c}) - 3)/9) \times 100$$

if score Q5c = 0,

$$\text{Score} = (((\text{score to Q4c} + \text{Q4d}) - 2)/6) \times 100$$

6. Personal Relationships:

if score Q5a + Q5b ≥ 2 ,

$$\text{Score} = (((\text{score to Q5a} + \text{Q5b}) - 2)/6) \times 100$$

if score Q5a + Q5b = 1,

$$\text{Score} = (((\text{score to Q5a} + \text{Q5b}) - 1)/3) \times 100$$

if score Q5a + Q5b = 0, treat as missing value (not applicable),

7. Emotions:

$$\text{Score} = (((\text{score to Q6a} + \text{Q6b} + \text{Q6c}) - 3)/9) \times 100$$

8. Sleep/energy:

$$\text{Score} = (((\text{score to Q7a} + \text{Q7b}) - 2)/6) \times 100$$

9. Incontinence severity measure:

$$\text{Score} = (((\text{score to Q8a} + \text{Q8b} + \text{Q8c} + \text{Q8d} + \text{Q8e}) - 5)/15) \times 100$$

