7.3. Multiple Comparisons / Multiplicity

Given the small sample size and exploratory nature of the efficacy study, no adjustment will be made for multiple comparison. Therefore, all the p-values presented will be nominal *P* value.

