KHQ scores for the nine domains will be calculated according to the Protocol Appendix. Change from baseline at each time point for the QoL endpoints will be analyzed and presented similarly to primary efficacy endpoint using linear mixed effect models in Tables 14.2.5.

We will tabulate the frequency and proportion of participant perception of response to treatment by time point and treatment group in Table 14.2.6. The Cochran–Armitage test will be used whether the treatment group has better response.

Exploratory Figures may also be generated for change from baseline by treatment for frequency of urination (Figure 14.2.1), volume of urination per day, number of incontinences episodes, and urgency (Figures 14.2.1.1 through 14.2.1.3) from voiding diary data, number of detrusor contractions (Figures 14.2.2). The contents and layout of the figure will be similar to that displayed in Figure 14.2, a figure for illustrative purpose only. Possibly other variables may be presented as figures if the data justifies the presentation.

Participant cystometry detailed measures from both overreader and site Investigators will be displayed in Listings 16.2.6.2.1 through 16.2.6.2.5.

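### KHQ Personal Relationships picks its formula by the sum Q5a + Q5b although 0 means not applicable: a patient with one applicable item cannot score above 33.3 and, if that item stays the same, loses 50% to 100% of any change

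*Protocol*

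**What the plan says.** In Protocol Appendix B, Q5a (relationship with partner) and Q5b (sex life) are each coded 0 for not applicable and 1 to 4 for increasing impact. Item 6 of the scoring section, Personal Relationships, has three branches, all chosen by the sum of the two codes:

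- "if score Q5a + Q5b ≥ 2": (sum − 2)/6 × 100, the two-item formula.
- "if score Q5a + Q5b = 1": (sum − 1)/3 × 100, the one-item formula.
- Sum of 0: missing.

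Item 5, Social Limitations, also contains a question that may not apply (Q5c), but it branches on that question's own code: "if score Q5c ≥ 1" selects a three-item formula, and a code of 0 selects a two-item formula with divisor 6. The domain under "2. Impact on life" rests on one question coded 1 to 4 and is scored (answer − 1)/3 × 100.

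SAP 9.2 takes the appendix as it stands: "KHQ scores for the nine domains will be calculated according to the Protocol Appendix". The resulting scores then enter a linear mixed model of their difference from baseline, as for the number of voids. No SAP section overrides the rule, and SAP 14 lists no change from the protocol's methods.

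**The concern.** A sum cannot tell how many items were answered when 0 is the code for not applicable. A sum of 4 may be two answers of 2, or one answer of 4 with the other item not applicable. Item 6 treats them alike. A patient with one applicable item who gives the worst possible answer therefore scores 33.3 out of 100, and a patient who answers 2 scores the same as one who answers 1.

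Because the analysis is of change from baseline, this compression carries into the treatment comparison. It acts in both directions: an improvement from 2 to 1 and a worsening from 1 to 2 both register as no change. With 6 patients per active dose and 6 pooled placebo patients, one affected patient can move a group mean noticeably.

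**Working it through.** **Inputs.** Codes 0 to 4 for Q5a and Q5b and the three branches of item 6 come from Protocol Appendix B. Group sizes (6, 6, 6 and pooled active 12) come from SAP 3.2. The plan gives no figure of its own to reproduce here.

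**Comparison rule.** The same formulas, selected by the number of applicable (non-zero) items: two applicable, (sum − 2)/6 × 100; one applicable, (answer − 1)/3 × 100; none, missing.

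**Step 1: scores with one applicable item.**

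| Answer | As printed | By item count |
|---|---|---|
| 1 | (1 − 1)/3 × 100 = 0 | 0 |
| 2 | (2 − 2)/6 × 100 = 0 | (2 − 1)/3 × 100 = 33.3 |
| 3 | (3 − 2)/6 × 100 = 16.7 | (3 − 1)/3 × 100 = 66.7 |
| 4 | (4 − 2)/6 × 100 = 33.3 | (4 − 1)/3 × 100 = 100 |

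There are 5 × 5 = 25 possible pairs. Six differ between the rules: answers 2, 3 and 4 on either item with the other at 0. The 16 pairs with both items applicable agree, as do the two pairs with a single answer of 1 (both score 0), and the pair with both at 0 is missing under either rule.

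**Step 2: comparison with item 5.** With Q5c at 0, the maximum of Social Limitations is (4 + 4 − 2)/6 × 100 = 100. With one item at 0, the maximum of Personal Relationships is (4 − 2)/6 × 100 = 33.3.

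**Step 3: change when the same single item applies at both visits.** Reverse changes mirror these.

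| Answers | Change as printed | Change by item count | Lost | Error (points) |
|---|---|---|---|---|
| 1 and 2 | 0 | 33.3 | 100% | 33.3 |
| 1 and 3 | 16.7 | 66.7 | 75% | 50.0 |
| 1 and 4 | 33.3 | 100 | 66.7% | 66.7 |
| 2 and 3 | 16.7 | 33.3 | 50% | 16.7 |
| 2 and 4 | 33.3 | 66.7 | 50% | 33.3 |
| 3 and 4 | 16.7 | 33.3 | 50% | 16.7 |

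Counting both directions, of 12 possible non-zero changes 2 lose 100%, 2 lose 75%, 2 lose 66.7% and 6 lose 50%. These are counts of possible answers, not probabilities.

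**Step 4: effect on a group mean.** Assume one such patient whose answer changes. Her error of 16.7 to 66.7 points is divided by the number scored in the group, which can be below 6 because patients with both items at 0 are missing.

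| Patients scored | Shift in mean change (points) |
|---|---|
| 3 | 5.6 to 22.2 |
| 4 | 4.2 to 16.7 |
| 5 | 3.3 to 13.3 |
| 6 | 2.8 to 11.1 |
| 12 (pooled active) | 1.4 to 5.6 |

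If her answer does not change, the error in change is 0.

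**The case against.** The arithmetic is not in dispute; the objections are to the benchmark and the weight.

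- **Appendix B may be the instrument's own algorithm.** The protocol presents it as such, and the scoring manual is not among the documents. If the manual prints the sum rule, re-scoring would depart from the instrument. This stands as a condition on the fix. It does not remove the inconsistency: item 6 contains a one-item formula that can return only 0, and item 5 handles the same situation by looking at the item itself.
- **Items 2 and 5 show a convention in other domains, not a rule for item 6.** That is true. The strongest evidence is item 6's own one-item branch; the other two items support it.
- **The loss range of 50% to 100% needs the same single item at both visits.** This stands. If applicability changes, the range does not hold: one answer of 4 followed by 3 on both items goes from 33.3 to 66.7 as printed, but from 100 to 66.7 by item count.
- **The size is hypothetical and the consequence small.** The documents give no frequency of exactly one item being not applicable. The 22.2-point figure needs only three scored patients and a full-range change in one of them. The shifts are in simple means, whereas the SAP uses a mixed model. The primary objective is adverse events, and SAP 7.3 declines multiplicity adjustment with the words "Given the small sample size and exploratory nature of the efficacy study". All this limits the weight of the point, but a rule that mis-scores a foreseeable answer pattern is still wrong as written.

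**Conclusion.** The concern holds. As printed, item 6 caps a patient with one applicable item at 33.3 and gives answers of 1 and 2 the same score. With that item unchanged across visits, she loses 50% to 100% of any change. One such patient with a changed answer shifts a 6-patient mean by 2.8 to 11.1 points, and the pooled 12 by 1.4 to 5.6.

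This rests on reading the one-item formula as intended for one applicable item, which the appendix itself supports and the scoring manual should confirm. It affects one of nine KHQ domains, in exploratory analyses with nominal p-values; the primary safety objective is untouched. If no patient has exactly one item not applicable, the effect is zero. No size is claimed for patients whose applicable items change between visits. The point should be corrected, but it does not threaten the trial's main purpose.

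**What to change.** First check the instrument's scoring manual. Unless it gives another rule, in which case use and state that one, write into SAP 9.2:

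- both Q5a and Q5b at least 1: ((Q5a + Q5b) − 2)/6 × 100;
- exactly one at least 1: (that answer − 1)/3 × 100;
- both 0: missing.

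Record this in SAP 14 as a change from the protocol. Settle it before the blind is broken, as SAP 2 requires for the plan and its deviations. Report by group and visit the number of patients with exactly one item not applicable, and show the printed-rule score as a sensitivity analysis. That analysis shows how much the rule matters here. Comparability with the earlier OAB trial is a weaker reason for it, because the KHQ domains that Protocol 1.4.2 names from that trial are General Health Perception and Impact on Life, which item 6 does not touch.

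The cost is one rule, one SAP 14 entry, one extra table and one count. No new data are needed: the item answers are collected, and KHQ is already listed per participant (Listing 16.2.6.5.1). Correcting Appendix B instead would make the SAP 14 entry unnecessary, but a protocol modification goes to the IRB and FDA (Protocol 12.3.2), so the SAP route is lighter.

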APPENDIX C. Participant Assessment of Disease and Response to Treatment

Site No. _____ Subject No. _____ Subject Initials _____ Date _____

1. Participant Assessment of Disease

Participants will rate their perceived bladder condition severity as follows:

Using validated 6-point rating scale participants will be asked the following.

“How bothersome do you consider your bladder problems? “

- 1- No problems
- 2 - Very minor problems
- 3 - Minor problems
- 4 - Moderate problems
- 5 - Severe problems
- 6 - Many severe problems

Improvement will be defined as a decrease of 1 point or more from baseline.

2. Participant Assessment of Response to Treatment

Participants' assessment of their response to treatment will be measured by asking:

"Has the treatment been of benefit to you?"

1. No benefit
2. Yes, a little benefit
3. Yes, very much benefit

Improvement will be defined as a decrease of 1 point or more from baseline.

Sign with Participant Initials: _____

Date Form Completed: _____

APPENDIX D. Cystometry Procedure Guidance

The importance of performing well-controlled cystometries cannot be over-emphasized. The methodology advocated by the International Continence Society in *Neurourology and Urodynamics* 21:261-274, 2002 should be followed.

Minimally, patients should be positioned in the sitting position. Using sterile aseptic techniques, a 7 or 8 Fr double-lumen transurethral catheter will be inserted into the urethra and a 9 Fr balloon catheter will be placed in the rectum to measure abdominal pressure. Room-temperature saline will be used at a filling rate of 50 ml/min. Either fluid filled catheters connected to pressure transducers or solid-state catheters should be used to help minimize artifact. The same system must be used for pre and post transfer studies on each patient. Participants should be instructed to neither void nor to try to inhibit micturition, but to simply report their sensations to the examiner. Participants should be instructed to indicate first desire to void, strong urge to void, and/or when they can no longer tolerate infusion (i.e. no longer delay micturition). Bladder filling should be discontinued as soon as the participant experiences a strong desire to void, uncomfortable fullness or pain.

Digitized recordings should be captured and stored for each participant. Waveforms from filling cystometries and pressure flow studies should be interpreted by a trained professional for each parameter noted in the following Table A. A cystometry overreader as well as the investigator will be required to interpret the results. The central overreader's interpretation will take priority. Printed waveforms should be kept with the patient's source records, with items such as artifacts and peak pressure measurements clearly identified. Digitized pressure recordings will be analyzed for the following parameters:

Table A: Cystometry Parameters and Definitions

Parameter	Description	Definition
DO; Yes/No	Detrusor overactivity ≥ 5 cm H ₂ O	Any involuntary contraction that has a pressure ≥ 5 cm H ₂ O (INCLUSION CRITERIA)
V _{First des} (mL)	Volume at first desire to void	The volume attained during filling cystometry that would lead the patient to pass urine at the next convenient moment but voiding can be delayed if necessary (ICS definition).
P _{det. open} (cm H ₂ O)	Detrusor pressure at beginning of voiding (prior to onset of first contraction (either volitional or involuntary))	Detrusor pressure at onset of the first detrusor contraction (either volitional or involuntary).
V _{1st} (mL)	Volume at first involuntary contraction; if detrusor overactivity (DO) present. Not applicable if no DO present.	Volume infused at the point of maximum detrusor pressure during the 1 st contraction. ¹
Det _{freq}	Total number of detrusor contractions during procedure (voluntary AND involuntary)	Total number of detrusor contractions including voluntary AND involuntary
Leak (Yes/no)	Was there a leak with overactivity	Involuntary detrusor contractions resulting in leak (NOT counting voluntary voids).
DO _{Leak freq}	Number of involuntary detrusor contractions resulting in leak (if DO present)	Number of involuntary detrusor contractions resulting in leak (if DO present). ¹
V _{leak} (mL)	If yes, Volume of each leak	Volume of each leak for each episode of leak ²
V _{leak cum} (mL)	If yes, cumulative volume of ALL leaks during procedure	Cumulative volume of leaks (calculated by computer from individual volumes) ²
DO _{No Leak freq}	Number of involuntary detrusor contractions NOT resulting in leak.	Total number of involuntary detrusor contractions that do not have an associated leak. ¹
P _{det Max} (cm H ₂ O)	Maximum detrusor pressure at involuntary contraction	Maximum amplitude of detrusor contraction during an involuntary contraction (if present) ³
P _{det 1st} (cm H ₂ O)	Maximum detrusor pressure at FIRST contraction	Max detrusor pressure at FIRST contraction (voluntary or involuntary). ¹
P _{Det Any} (cm H ₂ O)	Maximum detrusor pressure at ANY contraction	MAXIMUM detrusor pressure attained during the entire study (voluntary or involuntary). ⁴
Cys Cap (mL)	Cystometric Capacity: Volume at strong urge to void	The volume at which the patient feels that he/she can no longer delay micturition (has a strong desire to void). (ICS definition)
Q _{max} (mL / sec)	Peak flow rate during voiding (for both leaks and voluntary voids)	The Maximum rate of flow during any void (for both involuntary and voluntary voids)
V _{voided} (mL)	Total voided volume (leaks and voluntary)	Total volume voided for leak and volitional voids during the procedure
PVR (mL)	Post Void Residual Volume (PVR) (from catheterization)	Volume left in bladder after voiding at the conclusion of the study. This is measured by urodynamic catheterization.
(V _{total bladder}) (mL)	Total Bladder Volume (Total voided volume + catheterized PVR)	Post void residual volume + total voided volume (will be calculated)

DO_{dur} (seconds)	Duration of detrusor overactivity	Duration of MAXIMUM detrusor activity. ²
P_{Det}, Q_{Max} (cm H ₂ O)	Detrusor pressure at maximum flow during an involuntary contraction	Maximum detrusor pressure during terminal void (voluntary or involuntary). ²
$V_{bladder DO}$ (mL)	Bladder volume at each involuntary detrusor contraction	Infused bladder volume at the peak pressure of each involuntary contraction minus the amount leaked at each point for each involuntary contraction; Total will be calculated by the computer. ²
P_{abd} (cm H ₂ O)	Maximum abdominal pressure during any contraction	MAXIMUM abdominal pressure during ANY contraction. This will assess the abdominal straining component to voiding. ²

5. This is done by overreader, but not the sites
 
6. Done by site only
 
7. Detrusor pressure at first involuntary contraction is called “Detrusor Pressure” for sites on eCRF.
 
8. Maximum detrusor pressure at ANY contraction is called “Maximum Detrusor Pressure” for sites on eCRF.
		

**APPENDIX E. International Consultation on Incontinence
Questionnaire: Short Form¹.**

Site No.	Subject No.	Subject Initials _____	Date _____
How often do you leak urine?			
	Never		0
	About once a week or less often		1
	Two to three times a week		2
	About once a day		3
	Several times a day		4
	All of the time		5

We would like to know how much urine you think leaks. How much urine do you usually leak (whether you wear protection or not)?

None	0
A small amount	2
A moderate amount	4
A large amount	6

Overall how much does leaking urine interfere with your everyday life?
Please circle a number between 0 (not at all) and 10 (a great deal).

0	1	2	3	4	5	6	7	8	9	10
Not at all										A great deal

When does urine leak? (Please check all that apply)

Never - urine does not leak	D
Leaks before you can get to the toilet	D
Leaks when you cough or sneeze	D
Leaks when you are asleep	D
Leaks when you are physically active/exercising	D
Leaks when you have finished urinating and are dressed	D
Leaks for no obvious reason	D
Leaks all the time	D

Sign with Participant Initials: _____ Date Form Completed: _____

APPENDIX F. Participant Daily Diary

Please complete the information below **every day for the 7 days prior to your next scheduled visit.**

DAILY DIARY

Site #	Subject #	Subject initials
--------	-----------	------------------

Start Date: ___/___/___ to End Date: ___/___/___

#	Time of Urination (circle AM or PM)	Urgency (Scale 0-3) *	Was this an accident? Y/N	Volume (mL)**	#	Time of Urination (circle AM or PM)	Urgency (Scale 0-3) *	Was this an accident? Y/N	Volume (mL)**
1	: AM PM				11	: AM PM			
2	: AM PM				12	: AM PM			
3	: AM PM				13	: AM PM			
4	: AM PM				14	: AM PM			
5	: AM PM				15	: AM PM			
6	: AM PM				16	: AM PM			
7	: AM PM				17	: AM PM			
8	: AM PM				18	: AM PM			
9	: AM PM				19	: AM PM			
10	: AM PM				20	: AM PM			

****Urgency Scale**

0=None: No Urgency

1=Mild: Awareness of urgency or need to go to the bathroom *but easily tolerated*

2= Moderate: Enough urgency discomfort that it interferes with usual activities and tasks

3=Severe: Extreme urgency and discomfort that stops all activities and tasks

**** Urinate into supplied cylinder and measure the volume**

Number of pads used on this day: _____ (Daily pad count includes all pads newly applied during a calendar day- dates as above). Be sure to seal used pads **for 3 days prior to next visit** in the provided zip lock bag to bring to clinic at next visit.). Also bring one new clean pad for comparison.

To be completed at Study Center

Total number of urinations on this day _____

Mean volume per urination on this day _____

Sign with Participant Initials: _____

Date Form Completed: _____

APPENDIX G. Components and Guidelines for Health Status Questionnaire (SF-12)

SF-12 HEALTH SURVEY (STANDARD)⁵

Site No. _____ **Subject No.** _____ **Subject Initials** _____ **Date** _____

INSTRUCTIONS: This questionnaire asks for your views about your health. This information will help keep track of how you feel and how well you are able to do your usual activities.

Please answer every question by marking one box. If you are unsure about how to answer, please give the best answer you can.

In general, would you say your health is:

- Excellent**
 Very good
 Good
 Fair
 Poor

The following items are about activities you might do during a typical day. Does your health now limit you in these activities? If so, how much?

	Yes, Limited A Lot	Yes, Limited A Little	No, Not Limited At All
2. Moderate activities , such as moving a table, pushing a vacuum cleaner, bowling or playing golf			
3. Climbing several flights of stairs			

During the past 4 weeks, have you had any of the following problems with your work or other regular daily activities as a result of your physical health?

	Yes	No
4. Accomplished less than you would like		
5. Were limited in the kind of work or other activities		

⁵ Ware JE, Kosinski M, Keller, SD. SF-12: How to score the SF-12 Physical and Mental Health Summary Scales. Lincoln, RI: Quality Metric Incorporated, third Edition, 1998

During the past 4 weeks, have you had any of the following problems with your work or other regular daily activities as a result of any emotional problems (such as feeling depressed or anxious)?

- | | Yes | No |
|--|--------------------------|--------------------------|
| 6. Accomplished less than you would like |  |  |
| 7. Didn't do work or other activities as carefully as usual |  |  |
| 8. During the past 4 weeks , how much did pain interfere with your normal work (including both work outside the home and housework)? | | |
|  |  |  |
| Not at all | A little bit | Moderately |
|  |  |  |
| | Quite a bit | Extremely |

These questions are about how you feel and how things have been with you during the past 4 weeks. For each question, please give the one answer that comes closest to the way you have been feeling. How much of the time during the past 4 weeks

- | | All of the Time | Most of the Time | A Good Bit of the Time | Some of the Time | A Little of the Time | None of the Time |
|---|--------------------------|--------------------------|-------------------------------|--------------------------|-----------------------------|--------------------------|
| 9. Have you felt calm and peaceful? |  |  |  |  |  |  |
| 10. Did you have a lot of energy? |  |  |  |  |  |  |
| 11. Have you felt down-hearted and blue? |  |  |  |  |  |  |
| 12. During the past 4 weeks , how much of the time has your physical health or emotional problems interfered with your social activities (like visiting with friends, relatives, etc.)? | | | | | | |
|  |  |  |  |  |  |  |
| All of the time | Most of the time | Some of the time | A little of the time | None of the time | None of the time | None of the time |

Sign with Participant Initials: _____

Date Form Completed: _____
